4.2.1.2 Minor Protocol Deviations

Minor deviations will include, but are not limited to, the deviations presented in Table 4.2.

Table 4.2 - Definition of Minor Protocol Deviation Categories

Sub-Category	Description
Procedural violation	Violation of any study procedures not affecting safety or data evaluability
Time deviation (Plasma nicotine PK sample)	Assessments not taken at the correct time or within the allowed time window or date/time is missing (see Section 3.1)
Time deviation (other assessment)	Assessments not taken at the correct time or within the allowed time window or date/time is missing (see Section 3.1)
Assessment missing (Plasma nicotine PK sample)	Assessment is missing
Assessment missing (other assessment)	Assessment is missing
Randomized product sequence	Subject randomized not according to the sequence of the subject numbers assigned during the screening visit

4.2.1.3 Assessment Time Points and Assessment Time Windows

Assessment Time Points and Assessment Time Windows presented in Table 4.3.

Table 4.3 – Definition of Collection Time Points and Assessment Time Windows

Assessment	Nominal Time point(s)	Time Window
	(relative to T ₀)	
Plasma nicotine PK	5 minutes prior to T ₀	± 1 minute
samples	5 minutes after T ₀	± 1 minute
	10 minutes after T ₀	± 1 minute
	15 minutes after T ₀	± 1 minute
	20 minutes after T ₀	± 1 minute
	25 minutes after T ₀	± 1 minute
	30 minutes after T ₀	± 1 minute
	35 minutes after T ₀	± 1 minute
	40 minutes after T ₀	± 1 minute
	1 hour after T ₀	± 5 minutes
	3 hours after T ₀	± 5 minutes
	6 hours after T ₀	± 5 minutes
VAS craving, VAS liking	within 15 minutes prior to T ₀	N/A (VAS craving only)
"in the moment", VAS satisfaction "in the moment"	5 minutes after T ₀	± 1 minute
	10 minutes after T ₀	± 1 minute
	15 minutes after T₀	± 1 minute
	20 minutes after T ₀	± 1 minute
	25 minutes after T ₀	± 1 minute
	30 minutes after T ₀	± 1 minute
	35 minutes after T ₀	± 1 minute
	40 minutes after T ₀	± 1 minute
	1 hour after T ₀	± 5 minutes
	3 hours after T ₀	± 5 minutes; VAS craving and VAS satisfaction "in the moment" only
	6 hours after T ₀	± 5 minutes; VAS craving and VAS satisfaction "in the moment" only
VAS liking (overall) assessment	3 hours after T_{0M} and T_{0A}	± 5 minutes
VAS intention-to-use again	30 minutes after T ₀	± 1 minute
Ŭ	3 hours after T ₀	± 5 minutes

Statistical Analysis Plan Number CA36095

Assessment	Nominal Time point(s)	Time Window
	(relative to T₀)	
Product evaluation scale and the Sensory questionnaire	1 hour after T₀	± 5 minutes
Blood samples for λz	8 hours after T _{0A} on Day 2	± 5 minutes
	12 hours after T _{0A} on Day 2	± 5 minutes
ECG	Screening	N/A
	Day -1	N/A
	Day 3	N/A
	Early Termination	N/A
Vital signs	Screening	N/A
	Day -1	N/A
	Days 1, 2, and 3	Before T _{0M}
	Day 3 Discharge	N/A
	Early Termination	N/A

N/A = Not applicable

4.2.2 Data Summarization

Protocol deviations will be summarized in the SAF population by reporting the number and percent of subjects with protocol deviations, and the number of protocol deviations, will be summarized. Summaries will be broken down by main deviation category (major/minor), sub-categories, and evaluability impact. Subjects will be counted once per deviation category and can be counted for more than one deviation category.

4.3 Preliminary Data and Interim Analysis

There will be no interim analysis of this study data.

5. PRODUCT DESCRIPTIONS

The 4 variants of NP 1.0, Velo-NP and Zyn-NP will be provided by the Sponsor. The distribution will be controlled by the Investigator or a qualified and appropriately trained designee.

Statistical Analysis Plan Number CA36095

5.1 Test Products:

The following variants of NP 1.0 will be investigated in this study (Table 5.1).

Table 5.1 Test products

Name	Name in this study	Nicotine per pouch	рН	Moisture	Flavor
NP-1	NP-1	8.4 mg	8.0	30	Cool mint
NP-2	NP-2	8.4 mg	9.0	30	Cool mint
NP-3	NP-3	3.6 mg	8.0	15	Cool mint
NP-4	NP-4	3.6 mg	8.0	30	Cool mint

5.2 Comparator Products:

The following products will be used as the comparators (Table 5.2).

Table 5.2 Comparator products

Name	Name in this study	Nicotine per pouch	Flavor	
Velo® Ice Cool	Velo-NP	10 mg	Cool mint	
Zyn® Cool Mint Mini Zyn-NP Dry		3 mg	Cool mint	

6. PHARMACOKINETICS

6.1 Collection Schedule for Plasma Nicotine

The blood sample collection schedule for plasma nicotine is described in Table 6.1.

Table 6.1 Plasma Nicotine Samples Collection Schedule

Days 1,	Prior to start of product use in the morning (T_{0M}) and in the afternoon (T_{0A}) :		
2, and 3	T-1: 5 minutes (± 1 minute)		
(2 x 12			
blood	In relation to T_{0M} and T_{0A} :		
samples	T1 after 5 minutes (± 1 minute), T2 after 10 minutes (± 1 minute),		
on each	T3 after 15 minutes (± 1 minute), T4 after 20 minutes (± 1 minute),		
day)	T5 after 25 minutes (± 1 minute), T6 after 30 minutes (± 1 minute),		
	T7 after 35 minutes (± 1 minute), T8 after 40 minutes (± 1 minute),		
	T9 after 1 hour (± 5 minutes), T10 after 3 hours (± 5 minutes),		
	T11 after 6 hours (± 5 minutes).		
Day 2	Samples for determination of the terminal elimination half-life (t1/2z):		
(2 additio	In relation to T _{0A} from Day 2:		
nal blood	T1z after 8 hours (\pm 5 minutes) after T _{0A} ,		
samples)	T2z after 12 hours (\pm 5 minutes) after T _{0A} .		

6.2 Plasma Nicotine Concentrations

Samples will be analyzed for nicotine in plasma using a validated liquid chromatography coupled to tandem mass spectrometry (LC-MS/MS) detection analytical method with the appropriate quality controls in accordance with the Food and Drug Administration (FDA) Guidance for Industry: Bioanalytical Method Validation [1] and in accordance with FDA Good Laboratory Practice regulations (Title 21 CFR Part 58) at Bioanalytical Services

In general, values below the lower limit of quantification (LLOQ) will be imputed using 0.5 x LLOQ. For values above the upper limit of quantification (ULOQ), the ULOQ will be used for calculation and reporting in summary tables by the bioanalytical department.

Plasma concentrations as determined at the collection times described in Section 6.1 will be used for the calculation of the plasma nicotine PK parameters.

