12.1.4 Handling of Missing Values and of Values outside the Detection Limits

In general, missing data will not be imputed in this study, due to the nature of the measurements and the short periods of exposure and use. However, for questionnaire data, total scores and domain or subscale scores may use a certain degree of imputation by averaging across individual item scores. Further details will be provided in the SAP.

Nicotine concentrations outside detection limits will be substituted using the following rules:

- BLOQ values before T_0 will be imputed by LLOQ/2.
- BLOQ values after the last quantifiable value are not included in the analysis (e.g., for the calculation of AUC).
- Any BLOQ value (after T₀ and before the last quantifiable value) would need to be queried and, if confirmed, it will be imputed by LLOQ/2.

Handling of missing answers to questionnaires will be described in the SAP.

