6.3 Plasma Nicotine Pharmacokinetic Parameters

Nicotine PK parameters will be derived from background-corrected plasma nicotine concentration versus time data using a non-compartmental analysis (NCA) technique using appropriate and validated PK software (e.g., Phoenix WinNonlin version 8.1 or higher).

For nicotine concentrations below the LLOQ (BLQ) for the calculation of descriptive statistics of observed plasma nicotine concentrations:

- BLQ values before T0 will be imputed by LLOQ/2.
- BLQ values after the last quantifiable value are not included in the analysis (e.g., for the calculation of AUC).

• Any BLQ value (after T0 and before the last quantifiable value) would need to be queried* and, if confirmed, it will be imputed by LLOQ/2.

*The query will be triggered by data QC, and will query the bioanalytical laboratory. The information on the value queried and a summarized response from the bioanalytical laboratory will be part of the SDTM data (e.g. in the CO domain).

The number and percent of values below LLOQ or above ULOQ will be presented in each summary table.

To minimize the carry-over effect in the nicotine plasma PK parameters due to limited washout periods, the correction for background-concentration (baseline nicotine level obtained pre-use) will be applied to the concentration data. This correction will be implemented by calculating the nicotine exposure parameters using background-corrected concentration values as described below.

The nicotine terminal elimination rate constant λ_z (and $t_{1/2z}$) will be estimated including PK samples listed in Section 6.1 by using a linear regression on the log-transformed plasma nicotine concentration data. The regression analysis should contain data from at least 3 different time points in the terminal phase (including the last quantifiable concentration but excluding the concentration at T_{max}), consistent with the assessment of a straight line on the log-transformed scale. The nicotine plasma background-corrected PK parameters will be derived by performing the NCA on the background corrected concentrations.

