For the purposes of background-correction of the plasma concentrations post-baseline the following formula will be applied: $cC_t = C_t - C_0 \cdot *e^{-\lambda z \cdot t}$. Where, cC_t is the corrected concentration at each time point, C_t is the observed concentration at each time point, C_0 is the pre-use baseline concentration, λ_z is the Day 2 terminal elimination rate constant, t is the actual time since start of product use, and t is the actual time since the time of the pre-use baseline sample.

In particular, the following PK parameters will be derived from background-corrected nicotine levels following 30 minutes of product use:

C_{max}	Maximum background-corrected plasma concentration. C_{max} will be reported as long as there is at least one quantifiable concentration post T_0 .
T_{max}	Time to maximum background-corrected plasma nicotine concentration $C_{\text{\scriptsize max}}.$
AUC _{0-5min}	Area under the background-corrected plasma concentration-time curve from start of product use (T_0) to 5 minutes.
AUC _{0-10min}	Area under the background-corrected concentration-time curve from T0 to 10 minutes.
AUC _{0-15min}	Area under the background-corrected concentration-time curve from T0 to 15 minutes.
AUC _{0-20min}	Area under the background-corrected concentration-time curve from T0 to 20 minutes.

Statistical Analysis Plan Number CA36095

AUC _{0-25min}	Area under the background-corrected concentration-time curve from T0 to 25 minutes.
AUC _{0-30min}	Area under the background-corrected concentration-time curve from T0 to 30 minutes.
AUC _{0-35min}	Area under the background-corrected concentration-time curve from T0 to 35 minutes.
AUC _{0-40min}	Area under the background-corrected concentration-time curve from T0 to 40 minutes.
AUC _{0-1h}	Area under the background-corrected concentration-time curve from T0 to 1 hour.
AUC _{0-3h}	Area under the background-corrected concentration-time curve from T0 to 3 hours.
AUC _{0-6h}	Area under the background-corrected plasma nicotine concentration-time curve from T_0 to 6 hours.
$AUC_{0\text{-infinity}}$	Area under the background-corrected plasma nicotine concentration-time curve extrapolated from T0 to infinity.

All AUC parameters will be calculated using linear trapezoidal with linear interpolation method.

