For calculation of λ_z from observed data (to be used for background correction), concentrations BLQ will be set to 0 for pre-administration and prior to the first measurable concentration and set to missing after the last quantifiable concentration (if applicable).

The following steps will apply for the other PK parameters:

- Concentrations BLQ will be set to ½ the LLOQ except for any BLQ values after the last quantifiable concentration which will be set to missing.
- The formula for background correction will be applied.
- After the calculation, pre-product administration values will be assigned a value of zero in the analyses. All other values obtained will be reported as is even if these values are BLQ, except for any negative values, which will be set to zero.

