9. SUMMARY OF CHANGES FROM PROTOCOL-PLANNED ANALYSIS

In section 7.2 AUCs related to T1 to T11 for VAS craving assessment, VAS liking assessment and VAS satisfaction assessment have been added to the descriptive statistics.

In section 8.12, it is specified that the investigator will define ranges to determine normal or abnormal Spirometry results.

All other analyses described in this SAP are aligned with those analyses described in the protocol.

Statistical Analysis Plan Number CA36095

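### The SAP sets nicotine concentrations above the assay's upper limit to the limit itself; if peaks are capped, Cmax and affected AUCs are biased down and product ratios are attenuated toward 1.

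*SAP*

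**What the plan says.** For a concentration above the ULOQ, SAP 6.2 states that "the ULOQ will be used for calculation and reporting in summary tables", and names the bioanalytical department as the party doing so. The next sentence says that the plasma concentrations "will be used for the calculation of the plasma nicotine PK parameters".

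SAP 6.3 then sets out how out-of-range values enter the PK derivation, but only at the low end: "Concentrations BLQ will be set to ½ the LLOQ except for any BLQ values after the last quantifiable concentration". A low value inside a profile must also be queried with the laboratory. No step covers values above the ULOQ. The count of such values is reported: "The number and percent of values below LLOQ or above ULOQ will be presented in each summary table". The sensitivity analysis in SAP 6.5.2 deals with failed background correction, and the supplementary analysis in SAP 6.5.3 with high baselines. Neither deals with capped values.

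Protocol 12.1.4 introduces its rules with "Nicotine concentrations outside detection limits will be substituted using the following rules", but all of them concern values below the lower limit. SAP 9 lists two changes from the protocol, neither of them this one, and adds: "All other analyses described in this SAP are aligned with those analyses described in the protocol".

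**The concern.** A concentration above the ULOQ occurs at or near the peak, and more often for products that deliver more nicotine. Replacing it with a constant can only lower Cmax and the AUCs that include the sample, and it does so unequally across products. Comparing delivery between pouches is the first objective, and a Cmax ratio (NP-1 to Velo-NP) is the quantity used to describe precision. Protocol 2.1.2 says that NP 1.0 has not been tested in humans, so the plan holds no human data showing that peaks of the test variants stay below the limit.

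The tabulated counts would reveal capping but not correct it. The remedy is also time-limited: under Protocol 7.7, the nicotine samples are destroyed after database lock or finalization of the bioanalytical reports, whichever is later.

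**Working it through.** **Inputs.** From Protocol 12.9.5: geometric CV of Cmax 40% for all products, within-subject correlation 0.7 on the log scale, 24 subjects, precision 15% or less for NP-1:Velo-NP. From Protocol 12.9.4: 95% intervals. From SAP 5: contents of 8.4 mg (NP-1, NP-2), 3.6 mg (NP-3, NP-4), 10 mg (Velo-NP) and 3 mg (Zyn-NP). From Protocol 4.2: half-lives of 1.35 h (initial) and 17 h (terminal). Neither document gives a ULOQ or an expected concentration, so the ULOQ is varied as a multiple k of the geometric mean Cmax of the high-delivering product.

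**1. The plan's own figure.** σ = √ln(1 + 0.4²) = 0.3853. SE of the log ratio = 0.3853 × √(2(1 − 0.7)/24) = 0.0609. Half-width with t on 23 df = 0.1260. At a true ratio of 1 the expected interval is 0.882 to 1.134, a precision of 11.8% below and 13.4% above. This reproduces the stated 15% or less; the mean upper precision in 10,000 simulated trials was 13.3%.

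**2. Capping one product's Cmax.** With z = ln(k)/σ and p = 1 − Φ(z), capping changes mean log Cmax by −σ[φ(z) − z·p]. For k = 1.5: z = 1.052, p = 0.146, change = −0.3853 × (0.229 − 1.052 × 0.146) = −0.029, or −2.9%.

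**3. High/low ratio.** 400,000 paired log-normal Cmax values were simulated with low/high true ratios of 0.30, 0.36 and 0.43 (3/10, 3.6/10 and 3.6/8.4, assuming that Cmax is proportional to content). Results agreed within 0.3 percentage points across the three:

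| ULOQ / geometric mean Cmax | Peaks capped | High/low ratio | Low/high ratio |
|---|---|---|---|
| 1 | 50% | −14% | +16.5% |
| 1.25 | 28% | −6.5% | +6.9% |
| 1.5 | 15% | −2.9% | +2.9% |
| 2 | 3.6% | −0.6% | +0.6% |
| 3 | 0.2% | −0.03% | +0.03% |
| 5 | 0% | 0 | 0 |

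These match the one-product formula because the low product is almost never capped.

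**4. Two high-delivering products.** At k = 1.5 (relative to the reference product), a true ratio of 0.84 is seen as 0.855, 1.2 as 1.155, and 1.0 stays 1.0. Equal capping cancels in the point estimate.

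**5. Full profiles.** 20,000 profiles were simulated on the protocol's sampling grid with the SAP background correction, an assumed absorption profile, 5% sample error and a baseline near 10% of Cmax. Geometric mean Cmax changed by −20%, −9.5%, −4.4%, −0.9% and −0.04% at k = 1, 1.25, 1.5, 2 and 3. These exceed the figures in step 3 because the cap acts on the observed concentration, including background, and on the largest of several noisy samples. AUC0-10min did not change. AUC0-1h changed by −13% (k = 1) to −0.02% (k = 3), and AUC0-6h by −10% to −0.02%.

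**6. Tmax.** The correction subtracts C₀·exp(−λz·t), where "C_0 is the pre-use baseline concentration". A baseline below the lower limit is set to half that limit, so C₀ is positive and the subtracted term shrinks with time. If the true peak sample is not capped, the other values can only fall, and Tmax stays. If it is capped, every earlier sample is at most the ULOQ and has a larger amount subtracted, so none can overtake it; among tied capped values the last gives the corrected maximum. In simulated profiles with two or more capped samples, Tmax moved later in 26–31%, was otherwise unchanged, and was never earlier. The median Tmax did not move.

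**The case against.** **The effect may be nil.** No ULOQ is given, and nothing shows that any sample would exceed it. Protocol 2.1.2 says that pouches usually give a lower Cmax than cigarettes and that content did not track absorbed nicotine directly. This stands, and it is why the size is given only as a range.

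**The rule may concern only the laboratory's reporting.** The sentence ends with the bioanalytical department, SAP 6.3 has no above-ULOQ step, and a dilution procedure may sit in the bioanalytical plans cited in Protocol 7.5. That is possible, but the sentence names calculation as well as reporting, the next one sends concentrations into the PK parameters, and no text restores a measured value.

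**Filling a gap is not a change.** Protocol 12.1 leaves details to the SAP, and the rule contradicts no protocol rule. This is fair: SAP 9 needs only to record an addition.

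**Stronger readings that the documents do not support.** A reader might infer that ratios for strong pouches always fall. Velo-NP, at 10 mg, has the highest content and is a denominator, so capping it would raise ratios of weaker variants to it. A reader might also expect Tmax to be pulled to the first capped sample; step 6 shows the opposite direction. Nor do the documents show that the NP-1:Velo-NP ratio is biased: at the assumed ratio of 1, equal capping leaves it at 1. Capping also shrinks one product's log SD, but no ratio interval under capping was computed, so a too-narrow interval is not established.

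**Conclusion.** The point holds as a conditional defect. The SAP's rule can only lower Cmax and the AUCs that contain capped samples; it leaves Tmax unchanged or later, and attenuates toward 1 the ratios between unequally capped products. The size depends on the unstated ULOQ: a high/low Cmax ratio changes by about −14% at a ULOQ equal to the high product's geometric mean Cmax, −2.9% at 1.5 times, −0.6% at 2 times, and a negligible amount from 3 times upward. The 40% CV and 0.7 correlation are the protocol's; the ULOQ multiples, content-proportional Cmax, profile shape, sample error and baseline level are assumptions. The sample-size figure reproduces and is not affected. It cannot be concluded that truncation will occur, only that the plan would handle it poorly if it did.

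**What to change.** Replace the ULOQ sentence in SAP 6.2 with: samples above the ULOQ are diluted and re-assayed within the validated dilution range before sample destruction, and the diluted result is used for all PK parameters. State the ULOQ.

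Where re-assay is impossible, flag the affected parameters and run a sensitivity analysis that treats the capped value as a lower bound, for example a right-censored likelihood for log Cmax and the affected log AUCs. Do not delete those values. Under the log-normal model, deleting the top fraction p lowers the geometric mean by 1 − exp(−σφ(z)/(1 − p)): 4.1% at p = 0.05 and 7.2% at p = 0.10, against 0.8% and 1.8% for capping. A mixed model would recover part of this through within-subject correlation, but missingness caused by the value itself is not missing at random.

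List the rule in SAP 9 as an addition to Protocol 12.1.4, and align the bioanalytical plan.

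Cost: wording, a few re-assays from material already collected (4.0 mL of blood per nicotine sample, Protocol 7.7.1), and one sensitivity analysis that runs only if a capped value remains.

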6.3 Plasma Nicotine Pharmacokinetic Parameters

Nicotine PK parameters will be derived from background-corrected plasma nicotine concentration versus time data using a non-compartmental analysis (NCA) technique using appropriate and validated PK software (e.g., Phoenix WinNonlin version 8.1 or higher).

For nicotine concentrations below the LLOQ (BLQ) for the calculation of descriptive statistics of observed plasma nicotine concentrations:

- BLQ values before T0 will be imputed by LLOQ/2.
- BLQ values after the last quantifiable value are not included in the analysis (e.g., for the calculation of AUC).

• Any BLQ value (after T0 and before the last quantifiable value) would need to be queried* and, if confirmed, it will be imputed by LLOQ/2.

*The query will be triggered by data QC, and will query the bioanalytical laboratory. The information on the value queried and a summarized response from the bioanalytical laboratory will be part of the SDTM data (e.g. in the CO domain).

The number and percent of values below LLOQ or above ULOQ will be presented in each summary table.

To minimize the carry-over effect in the nicotine plasma PK parameters due to limited washout periods, the correction for background-concentration (baseline nicotine level obtained pre-use) will be applied to the concentration data. This correction will be implemented by calculating the nicotine exposure parameters using background-corrected concentration values as described below.

The nicotine terminal elimination rate constant λ_z (and $t_{1/2z}$) will be estimated including PK samples listed in Section 6.1 by using a linear regression on the log-transformed plasma nicotine concentration data. The regression analysis should contain data from at least 3 different time points in the terminal phase (including the last quantifiable concentration but excluding the concentration at T_{max}), consistent with the assessment of a straight line on the log-transformed scale. The nicotine plasma background-corrected PK parameters will be derived by performing the NCA on the background corrected concentrations.

For the purposes of background-correction of the plasma concentrations post-baseline the following formula will be applied: $cC_t = C_t - C_0 \cdot *e^{-\lambda z \cdot t}$. Where, cC_t is the corrected concentration at each time point, C_t is the observed concentration at each time point, C_0 is the pre-use baseline concentration, λ_z is the Day 2 terminal elimination rate constant, t is the actual time since start of product use, and t is the actual time since the time of the pre-use baseline sample.

In particular, the following PK parameters will be derived from background-corrected nicotine levels following 30 minutes of product use:

C_{max}	Maximum background-corrected plasma concentration. C_{max} will be reported as long as there is at least one quantifiable concentration post T_0 .
T_{max}	Time to maximum background-corrected plasma nicotine concentration $C_{\text{\scriptsize max}}.$
AUC _{0-5min}	Area under the background-corrected plasma concentration-time curve from start of product use (T_0) to 5 minutes.
AUC _{0-10min}	Area under the background-corrected concentration-time curve from T0 to 10 minutes.
AUC _{0-15min}	Area under the background-corrected concentration-time curve from T0 to 15 minutes.
AUC _{0-20min}	Area under the background-corrected concentration-time curve from T0 to 20 minutes.

Statistical Analysis Plan Number CA36095

AUC _{0-25min}	Area under the background-corrected concentration-time curve from T0 to 25 minutes.
AUC _{0-30min}	Area under the background-corrected concentration-time curve from T0 to 30 minutes.
AUC _{0-35min}	Area under the background-corrected concentration-time curve from T0 to 35 minutes.
AUC _{0-40min}	Area under the background-corrected concentration-time curve from T0 to 40 minutes.
AUC _{0-1h}	Area under the background-corrected concentration-time curve from T0 to 1 hour.
AUC _{0-3h}	Area under the background-corrected concentration-time curve from T0 to 3 hours.
AUC _{0-6h}	Area under the background-corrected plasma nicotine concentration-time curve from T_0 to 6 hours.
$AUC_{0\text{-infinity}}$	Area under the background-corrected plasma nicotine concentration-time curve extrapolated from T0 to infinity.

All AUC parameters will be calculated using linear trapezoidal with linear interpolation method.

For calculation of λ_z from observed data (to be used for background correction), concentrations BLQ will be set to 0 for pre-administration and prior to the first measurable concentration and set to missing after the last quantifiable concentration (if applicable).

The following steps will apply for the other PK parameters:

- Concentrations BLQ will be set to ½ the LLOQ except for any BLQ values after the last quantifiable concentration which will be set to missing.
- The formula for background correction will be applied.
- After the calculation, pre-product administration values will be assigned a value of zero in the analyses. All other values obtained will be reported as is even if these values are BLQ, except for any negative values, which will be set to zero.

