6.4 Pharmacokinetic Data Summarization and Presentation

SAS software (Version 9.4, Cary, North Carolina) will be used for all data presentation and summarization including statistical analyses, summary tables, graphs, and data listings.

Plasma nicotine concentrations (observed and background-corrected), λ_z (observed only), and other PK parameters (background-corrected only) will be summarized with descriptive statistics including number of subjects (n), number and percent of subjects with missing data (Missing, n (%)), arithmetic mean (Mean), standard deviation (SD), percent CV (CV%), standard error of the mean (SEM), minimum, first quartile (Q1), median, third quartile (Q3), and maximum.

Statistical Analysis Plan Number CA36095

In addition, geometric mean (Geo. Mean), 95% geometric confidence interval (Geo. 95% CI), and geometric CV (Geo. CV%) will be presented, as applicable.

For observed plasma nicotine concentrations, the number and percent of values below LLOQ (BLQ, n(%)) and above ULOQ (ALQ, n(%)) will be presented in each summary table.

Categorical variables will be summarized by frequency statistics (number and percentage).

For endpoints relating to sampling times (e.g., T_{max}) only n, missing n (%), median, Q1, Q3, minimum and maximum will be presented.

All analyses and summaries will be performed by product and overall. Summaries will be further stratified by sex.

The analytical data will be presented in the tables/listings to the same precision as received from the analytical laboratory.

The level of precision and rounding for the summary statistics will be specified in the TFL shell document.

Where individual data points are missing because of dropouts or other reasons, the data will be summarized based on reduced denominators. Missing PK data will be treated as missing, and no data imputation will be conducted.

Mean and individual plasma nicotine concentrations will be presented graphically (linear and semi-log plots; linear plots will be presented with and without SD).

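### Does AUC0-infinity lack a usable terminal slope in the five product uses that are sampled only to 6 hours?

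*SAP*

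**What the plan says.** SAP 6.1 gives every use 12 samples, the last being "T11 after 6 hours (± 5 minutes". Only the Day 2 afternoon use has later samples, at 8 h and 12 h.

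SAP 6.3 says the terminal rate constant λz is "estimated including PK samples listed in Section 6.1 by using a linear regression" on log concentrations, and adds: "The regression analysis should contain data from at least 3 different time points in the terminal phase". In the background-correction formula λz "is the Day 2 terminal elimination rate constant". The rules for values below quantification refer to λz calculated "from observed data (to be used for background correction". The corrected "PK parameters will be derived by performing the NCA on the background corrected concentrations".

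AUC0-infinity is defined as "Area under the background-corrected plasma nicotine concentration-time curve extrapolated from T0 to infinity", with linear trapezoids for all AUCs and no stated slope for the tail.

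SAP 6.4 lists λz and the remaining parameters with the labels "observed only), and other PK parameters (background-corrected only". SAP 6.5.2 treats the terminal elimination rate as one quantity per subject and gives a same-sex average as a substitute.

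Protocol 4.2 gives half-lives of 1.35 h and 17 h, starts the terminal phase at 8 to 10 h, and derives the terminal rate from sampling on Day 2 and Day 3.

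**The concern.** Read sentence by sentence, the SAP ties its only λz to background correction and sends every other parameter through non-compartmental analysis of the corrected profiles. An analyst could then take one of three routes:

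- Fit a slope to each corrected profile. The samples end at 6 h, so this would be a fast-phase slope.
- Apply the three-point rule strictly and leave AUC0-infinity missing for five uses out of six. SAP 6.4 allows no imputation.
- Carry the subject's Day 2 λz to all six uses.

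AUC0-infinity enters the main ANOVA. It is also the only PK endpoint that Objective 4 pairs with the Product Evaluation Scale and the Sensory questionnaire. The by-product ANCOVAs in SAP 7.3 compare subjects with one another, so error in a subject's λz does not cancel there. If the routes gave very different values, the reported exposure would depend on an undocumented choice.

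**Working it through.** **1. Sampling.** SAP 6.1 gives 3 days × 2 uses × 12 samples + 2 = 74 samples. At 4.0 mL each this is 296 mL, which matches Protocol 7.7.1 exactly. There are no other late samples.

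**2. Terminal-phase points, counted from 8 h.**

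| Use | Own samples | With the next use's pre-use sample |
|---|---|---|
| Day 2 afternoon | 2 (8 h, 12 h) | 3 (Day 3 morning) |
| Each of the other five | 0 | at most 1 |

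The Day 3 morning pre-use sample is among those listed in SAP 6.1, and Protocol 4.2 names Day 3. The three-point rule can therefore be met once per subject, but not once per use.

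**3. Which λz the text supports.** The SAP mentions only the Day 2 constant, summarises it from observed data only, and treats it as one value per subject in 6.5.2. A separate λz for each corrected profile is neither described nor scheduled for summary. Leaving five uses empty would contradict listing AUC0-infinity as an endpoint for all six products.

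**4. Size of the choice without assay error or carry-over.** The tail is C(6 h)/λ.

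- Half-life 1.35 h: λ = ln 2/1.35 = 0.5134 per h, so the tail is 1.95 × C(6 h).
- Half-life 17 h: λ = ln 2/17 = 0.0408 per h, so the tail is 24.5 × C(6 h).

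That 12.6-fold gap is an outer bound. For a profile take C(t) = R·exp(-0.5134t) + exp(-0.0408t), where R is an assumed fast-to-slow amplitude ratio. For R = 5:

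- True AUC0-infinity = 5/0.5134 + 1/0.0408 = 34.26. AUC0-6h = 14.61 and C(6 h) = 1.013.
- Own slope from 1, 3 and 6 h is 0.268. 14.61 + 1.013/0.268 = 18.4, which is 46% low.
- Subject slope from 8, 12 and 15.4 h is 0.0551. 14.61 + 1.013/0.0551 = 33.0, which is 4% low.

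| R | Beyond 6 h | Own slope (1, 3, 6 h) | Subject λz (third point 15.4 h / 13.9 h) |
|---|---|---|---|
| 3 | 64% | -50% | -3.0% / -5.6% |
| 5 | 57% | -46% | -3.8% / -7.0% |
| 10 | 46% | -37% | -4.2% / -7.9% |
| 20 | 33% | -26% | -3.5% / -6.9% |
| 99 | 13% | -8% | -0.2% / -2% |

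The third-point times follow from an assumed 8.5 h or 10 h between the morning and afternoon uses: 24 - 8.5 - 5/60 = 15.4 h and 24 - 10 - 5/60 = 13.9 h.

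**5. With six uses, carry-over and background correction.** The inputs are zero-order uptake over 30 minutes, all scheduled samples, the SAP's correction formula, negatives set to zero, linear trapezoids, and R from 3 to 20. Without assay error the bias is -20% to -50% with the own slope and +5% to +19% with the subject λz. The subject-λz bias differs by at most 7 points across a subject's uses. At the upper end this is a factor of about 1.19/1.12 = 1.06 between two uses, before the sequence balance and the period term act on it.

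**6. Noise.** At an assumed assay CV of 10%, the log SD of the error is:

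| | Subject λz | Own slope |
|---|---|---|
| Within subject | 0.10-0.22 | 0.07-0.19 |
| Total | 0.15-0.32 | 0.07-0.21 |

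The squared correlation with true log AUC0-infinity bears on the by-product ANCOVAs. With an assumed 30% between-subject variation in R and in the terminal rate, it is:

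| Assay CV | Subject λz | Own slope |
|---|---|---|
| 5% | 0.89-0.97 | 0.75-0.91 |
| 10% | 0.55-0.83 | 0.63-0.90 |
| 15% | 0.38-0.61 | 0.48-0.88 |

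**The case for a change.** The best case for a change is that two competent programmers could deliver AUC0-infinity levels differing by up to about half. One sentence naming the subject's λz and its three samples would prevent this, with no new data. It would also stop the slope being chosen after the results are seen. All of this stands as a remark on wording: the SAP has no such sentence, and λz is introduced mainly for background correction.

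Three things weaken it as a demand for change. First, the sentence would record what the plan already implies. Second, against the fast-phase reading it is a trade-off. It repairs the level, but at 10% assay CV or above it makes the by-product associations, the analysis said to be most exposed, less precise. A bias shared by all subjects does not alter the percentage of variance explained, whereas noise does. Third, fixing exactly three samples would be fragile, because Protocol 4.2 warns that the last may be unquantifiable and that four points are likely to be needed.

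Two additions have also been considered. The percentage extrapolated is a reporting item; where the 6 h sample is quantifiable it is 1 - AUC0-6h/AUC0-infinity, and both endpoints are already reported. Adding AUC0-6h to the Product Evaluation Scale and Sensory models would depart from Objective 4, and its benefit depends on inputs the documents do not give. With no between-subject variation in R and terminal rate, AUC0-6h does better even at 5% assay CV (0.98-0.99 against 0.89-0.97). With 50% variation, AUC0-infinity does better at 10% CV for R = 3 and 5 (0.60 and 0.64 against 0.49 and 0.56).

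**Conclusion.** The SAP leaves the extrapolation slope unstated, but its text points to one answer: the subject's single observed λz, applied to all six uses. Under that reading the level error is about -8% to +19% for amplitude ratios of 3 to 20, and most of it cancels in product ratios. The larger error of about -20% to -50% needs a per-use slope that the plan does not describe, and it shrinks to about -8% if the slow phase is small (R = 99). The study is exploratory, with no hypothesis and no significance level. The remaining imprecision of AUC0-infinity comes from sampling to 6 h, which wording would not cure.

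The conclusion that the text supports one λz rests on the documents alone. The sizes rest on the protocol's half-lives and on assumed amplitude ratios, assay CVs, spacing of uses and between-subject variation. They also assume the same average uptake in every use and ignore nicotine left from earlier smoking. No change to the plan follows.
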